## **4.2 Subject Demographics and Other Baseline Characteristics**

### **4.2.1 Demographic Characteristics**

Descriptive statistics [number of subjects (n), mean, SD, median, minimum and maximum for continuous variables, frequency count (n) and percentage (%) of subjects for categorical variables] will be presented for demographic characteristics by treatment group and overall. These variables include gender, race, ethnicity and age (years), and will be presented for the Safety population ([Table 14.1.3.1](#)), the mITT population ([Table 14.1.3.2](#)) and if applicable, for the PP population ([Table 14.1.3.3](#)).

Demographic information will be listed for all randomized subjects in [Listing 16.2.4.1.1](#).

### **4.2.2 Baseline Characteristics**

Descriptive statistics (n, mean, SD, median, minimum and maximum for continuous variables, n and % of subjects for categorical variables) will be presented for baseline characteristics by treatment group and overall. Baseline characteristics presented for the Safety population ([Table 14.1.4.1](#)) include denture material type (acrylic or cobalt chrome), baseline mean MGI score and category (low:  $\leq 2.0$ /high:  $>2.0$ ) and the number and percentage of subjects included in each stratum as described in [Section 3.2](#) (Subgroups/Stratifications). Baseline characteristics will also be presented for the mITT population ([Table 14.1.4.2](#)) and, if applicable, for the PP Population ([Table 14.1.4.3](#)).

Baseline characteristics will be listed for all randomized subjects in [Listing 16.2.4.1.2](#).

### **4.2.3 General Medical History**

Medical history data will be listed ([Listing 16.2.4.2](#)) for all randomized subjects with start date and end date or ongoing at the start of the study.

### **4.2.4 Dental History**

Descriptive statistics (n, mean, SD, median, minimum and maximum for continuous variables; n and % of subjects for categorical variables) will be presented for dental history by treatment group and overall.

Data collected on dental history and the RPD will be summarized for the Safety population ([Table 14.1.5.1.1](#)) and mITT population ([Table 14.1.5.1.2](#)), and includes the the number of teeth replaced by RPD, number of abutment teeth, duration of RPD use (years), the duration of the current RPD use (years), whether the subject normally sleeps with RPD in place (Yes/No), type of RPD based on the Kennedy Classification, the subject's overall satisfaction with the RPD and the cause of tooth loss leading to the RPD. These data will also be listed in [Listing 16.2.4.3.2](#) for all randomized subjects.

Baseline data collected regarding the subject's current oral hygiene product usage will be summarized for the Safety population ([Table 14.1.5.2.1](#)) and mITT population

([Table 14.1.5.2.2](#)), including the frequency of current toothpaste, mouthrinse and denture cleanser usage. These data will also be listed in [Listing 16.2.4.3.4](#) for all randomized subjects.

The tooth numbers replaced by the RPD, the abutment teeth and the missing natural teeth will be presented in [Listing 16.2.4.3.1](#) for all randomized subjects.

Data from the evaluation of well-fit partial denture and well-made partial denture will be listed in [Listing 16.2.4.3.3](#) for all randomized subjects.

#### **4.3 Treatments (Study Product, Rescue Medication, other Concomitant Therapies, Compliance)**

Randomization details will be listed, including the planned study treatment, the actual study treatment the subject was randomized to and the randomization date ([Listing 16.1.7.1](#)).

Batch numbers also will be listed, including Randomization Number, Bulk Kit Description, Date Dispensed, Visit, Lot ID and Quantity ([Listing 16.1.6.1](#)).

##### **4.3.1 Study Treatment Compliance and Exposure**

Product compliance will be recorded as the total number of brushing, mouth rinsing and denture cleaning occasions since the last visit. In addition, any missed or additional brushing, mouth rinsing or denture cleaning occasions since the last visit are collected for the Intervention Group and any deviation from the normal hygiene range or change in oral hygiene products are collected for the No Intervention Group.

Treatment exposure will be calculated for each visit interval and overall treatment duration as follows:

- Treatment Exposure (Days) = Visit Interval End Date – Visit Interval Start Date.

Compliance will be calculated for the Intervention Group for brushing, mouth rinsing and denture cleaning for each visit interval and overall as:

- Brushing/Mouth Rinsing/Denture Cleaning Compliance (%) = [(Number of Brushing/Mouth Rinsing/Denture Cleaning occasions) / (Treatment Exposure x 2)] x 100.

Overall exposure and compliance will be calculated from Visit 2 (Day 0) to Visit 4 (Week 12) [or the last available visit for subjects who discontinue prior to Visit 4 (Week 12)].

The number of brushing occasions, mouth rinsing occasions, denture cleaning occasions will be summarized by treatment group using descriptive statistics (n, mean, SD, median, minimum and maximum) for each visit interval and overall study treatment duration, in [Table 14.2.1.1.1](#) for the Safety population and [Table 14.2.1.1.2](#) for the mITT population. In addition, the percentage compliance (n, mean, SD, median, minimum and maximum) and the number and percentage of subjects <80%, between 80% - 120% and >120% compliant will also be presented for brushing, mouth rinsing and denture cleaning for the Intervention Group.

Treatment exposure (days) will be summarized by treatment group using descriptive statistics (n, mean, SD, median, minimum and maximum), for each visit interval and overall study treatment duration, in [Table 14.2.1.2.1](#) for the Safety population.

Compliance and exposure data will be listed for all randomized subjects, including the start and end date and exposure (days) for each visit interval and overall. For subjects randomized to the Intervention Group ([Listing 16.2.5.1](#)), data listed for brushing, mouth rinsing and denture cleaning will include the number of occasions, the number of missed and additional brushing, mouth rinsing and denture cleaning occasions and the percentage compliance for each visit interval and overall. For subjects randomized to the No Intervention Group ([Listing 16.2.5.2](#)), data listed will include any deviation from the normal oral hygiene routine and change in oral hygiene products for each visit interval and the number of brushing, mouth rinsing and denture cleaning occasions for each visit interval and overall.

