## **7 DISCONTINUATION OF STUDY INTERVENTION AND SUBJECT DISCONTINUATION/WITHDRAWAL**

### **7.1 Subject Discontinuation/Withdrawal**

A subject may withdraw from the study at any time at his or her own request or may be withdrawn at any time at the discretion of the investigator or sponsor for safety, behavioral reasons, or the inability of the subject to comply with the protocol-required schedule of study visits or procedures.

The following circumstances require discontinuation of study product and/or premature subject withdrawal:

- Protocol violation that may impact the subject's safety
- Withdrawal of informed consent
- Subject lost to follow-up
- Unblinding of the subject
- Pregnancy

Property of GSK Consumer Healthcare - Confidential

May not be used, divulged, published or otherwise disclosed without the consent of GSKCH

SP1963/SOP-208661: Template Version: 14 Mar 2019

---

If a subject is discontinued or prematurely withdraws from the study, the reason(s) for discontinuation or withdrawal and the associated date must be documented in the relevant section(s) of the CRF.

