### **8.2.2 Visit 3/Day 42 ±3**

Procedures will be conducted by the Investigator, or suitably qualified designee.

Subjects will undergo, in the following order (wherever possible), and findings documented in the CRF:

1. Changes in health, medication and non-drug treatments/procedures will be documented in the CRF.
2. Spontaneous reporting of adverse events and those elicited by asking subjects to respond to a non-leading question such as "How do you feel?" will be assessed.
3. Study products and diaries collected from subjects. Staff will complete visual checks of the returned lead-in toothbrush/toothpaste and review the completed diary. Any suspected over or under use and the number of any missed or additional product usage will be documented in the CRF.
4. Subjects compliance with treatment and denture cleaning assessed through examination of subject diary and product usage.
5. Subject completes the questionnaire.
6. Subject removes RPD.
7. RPD is assessed for PDCI.
8. For a subset of subjects an image(s) of their RPD will be taken. This is only to be performed at this visit should insufficient images of acceptable quality not have been obtained at Visit 2.

Property of GSK Consumer Healthcare - Confidential

May not be used, divulged, published or otherwise disclosed without the consent of GSKCH

SP1963/SOP-208661: Template Version: 14 Mar 2019

---

9. Subject undergoes a full OST examination.
10. Subject continuance assessed.
11. Subject undergoes MGI assessment including a repeat assessment if required.
12. Subject undergoes CI assessment.
13. Subject undergoes plaque disclosure and TPI assessment including a repeat assessment if required.
14. Subject undergoes ODI assessment.
15. Subject undergoes BI assessment.
16. The subject's RPD will be returned.
17. Intervention group only - study products will be dispensed, including sundry items, product usage instructions and their diary returned to subject. Subject to perform supervised product usage and study staff to review instructions on correct product use with the subject for at home use.
18. No intervention group only – subject to receive only their returned diary.
19. AEs and incidents recorded.

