### **3.4 Timepoints and Visit Windows**

The timepoints, visits and visit windows for this study are defined in [Table 1-1](#), “Schedule of Activities”. Deviations from the scheduled assessment times should be avoided or kept to a minimum as far as possible. Any deviation from the study schedule may be reviewed on a case-by-case basis at the Blind Data Review Meeting (BDRM) before database lock to determine whether the data should be excluded from the Per Protocol (PP) population.

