#### **4.1.1 Subject Disposition**

Screen failures will be defined as subjects who consent to participate in the clinical study but are not subsequently randomized. An enrolled subject is a subject who has signed informed consent and is eligible to proceed beyond the screening visit.

The number of subjects screened, enrolled and randomized will be presented in [Table 14.1.1](#). The number and percentage of screen failure subjects (subjects not randomized) with reasons why subjects are not randomized will also be displayed. Percentages for screen failure subjects will be based on the total number of subjects screened.

The number and percentage of subjects who complete and discontinue the study, broken down by reason for discontinuation, will be presented by treatment group and overall in [Table 14.1.1](#). The percentages will be based on the number of subjects randomized.

[Table 14.1.1](#) will also present the number and percentage of subjects in each of the defined analysis populations by treatment group and overall. Percentages will be based on the number of subjects randomized in the relevant treatment group or overall.

Subject disposition including demographic data (age, gender and race), screening date, study treatment start date (Visit 2, Day 0), the subject status (completer, Yes/No), date of study completion or withdrawal, duration (in days) in the study (defined as [(date of completion or

withdrawal – study treatment start date) + 1], the primary reason for withdrawal and further details for withdrawal will be listed ([Listing 16.2.1.1](#)).

Subject disposition information will be listed for non-randomized subjects ([Listing 16.2.1.2](#)), including demographic information (age, gender and race), screening date, reason for screen failure and any further details of reason for screen failure.

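### SAP 4.3.1 closes exposure and compliance at the last available visit, so withdrawers who do not return get 0 days, or only the days to Visit 3

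*SAP*

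**What the plan says.** SAP 4.3.1 defines exposure by visit interval: "Treatment Exposure (Days) = Visit Interval End Date – Visit Interval Start Date". Compliance, for the Intervention Group only, divides the number of brushing, rinsing or denture cleaning occasions by twice that exposure (the formula closes with "Treatment Exposure x 2)] x 100"). For the whole study, "Overall exposure and compliance will be calculated from Visit 2 (Day 0) to Visit 4 (Week 12"), and a bracket adds "or the last available visit for subjects who discontinue prior to Visit 4 (Week 12").

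SAP 3.4 says which visits exist: "The timepoints, visits and visit windows for this study are defined in" Table 1-1. That table has Visits 1 to 4 and no early-termination visit. Between Day 0 and Week 12 there is only the visit that the protocol heads "Visit 3/Day 42 ±3".

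The withdrawal date is available. Protocol 7.1 states that "the reason(s) for discontinuation or withdrawal and the associated date must be documented in the relevant section(s) of the CRF". SAP 4.1.1 already uses it in the disposition listing, which gives "the subject status (completer, Yes/No), date of study completion or withdrawal, duration (in days) in the study", computed as the completion or withdrawal date minus the treatment start date, plus 1.

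SAP 4.3.1 has no rule for zero exposure, for an interval cut short by withdrawal, or for product use after the last visit.

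**The concern.** A subject can use the products for weeks after Visit 2 or Visit 3 and then leave without returning. Under SAP 4.3.1 those weeks do not exist. The Safety population needs only one dose, so the subject stays in the Safety exposure table (14.2.1.2.1) with a value that is too low. The compliance percentage is undefined, or is computed over a period shorter than the one in which product was due.

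The errors fall on early leavers, the group for whom a reader of a safety and tolerability study most wants to know how long the products were used. Two outputs of the same report would also give very different day counts for one person, with nothing to explain the gap.

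**Working it through.** **Inputs.** Exposure E = interval end date − start date (SAP 4.3.1). Compliance = 100 × occasions / (2E) (SAP 4.3.1). Days in study = withdrawal date − start date + 1 (SAP 4.1.1). Visit 3 falls on Day 42 ±3, that is Day 39 to 45. Compliance bands are below 80%, 80% to 120%, and above 120% (SAP 4.3.1). Full use is two occasions a day.

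**Check on completers.** The plan states no exposure or compliance figure to reproduce. For Visit 4 on Day 84 with full use, E = 84 and compliance = 168 / (2 × 84) = 100%. Day 81 and Day 87 also give 100%. The formula works for completers.

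**Withdrawal after Visit 2, no later visit.** The last available visit is Visit 2, so E = 0 − 0 = 0 and compliance = occasions / (0 × 2), undefined. A Day 30 withdrawer has 30 − 0 + 1 = 31 days in study under 4.1.1 and 0 days of exposure under 4.3.1. The +1 accounts for one day of that gap and the end date for the other 30.

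**Withdrawal between Visits 3 and 4, no later visit.** E is the day of Visit 3.

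| Withdrawal day | Visit 3 day | Exposure under 4.3.1 | Days lost |
|---|---|---|---|
| 60 | 42 | 42 | 18 (30%) |
| 75 | 42 | 42 | 33 (44%) |
| 75 | 39 | 39 | 36 (48%) |
| 75 | 45 | 45 | 30 (40%) |

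**Compliance for the Day 75 withdrawer, Visit 3 on Day 42.** The SAP does not say whether uses after Visit 3 count.

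- If they count and use was full: 2 × 75 = 150 occasions over 2 × 42 = 84 expected gives 150/84 = 178.6%, in the above-120% band. In general 2w/84 exceeds 1.2 once w exceeds 50.4, so any fully compliant subject who withdraws after Day 50.4 is flagged as over-using (46.8 to 54.0 across the Visit 3 window).
- If they do not count and the subject stopped at Visit 3: 84/84 = 100%. Over the time actually in the study it is 84/150 = 56%, in the below-80% band.

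**How many.** The plan gives no expected withdrawal count. The allowance is 150 − 128 = 22 (14.7%), or 175 − 128 = 47 (26.9%) at the maximum. No split before and after Week 6 is given.

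**The case against.** The strongest reply is that the last available visit is not defined. Protocol 7.2 lets the site request a final visit with return of products, and SAP 1.1 allows unplanned visits. If such a visit counts, exposure is neither 0 nor cut back to Visit 3. This stands: the point applies to subjects who attend no later visit, and it is wrong to infer that every early withdrawer gets 0 days. But the final visit is optional, and the SAP does not say that it counts.

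Second, for a subject who never returns, compliance is largely a data gap. Protocol 8.2.4.1 has occasions recorded for the time since the previous visit, so with no diary there is no numerator, whatever the end date. This also stands, but it does not excuse 0 days of exposure when the withdrawal date is known.

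Third, days in study and treatment exposure are different quantities. That is fair, so 31 against 0 is not a contradiction in definition. It does show that the plan holds the date it needs and does not use it.

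Stronger readings are tempting but not supported:

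- That mean compliance is made to look better. The direction depends on whether later uses are counted; one reading inflates past 120%, the other hides non-use.
- That these subjects disappear. SAP 4.3.1 lists compliance and exposure for all randomized subjects.
- That the below-80% band decides important deviations. SAP 4.1.2 leaves the criteria to the Blind Data Review Plan and the Protocol Deviation Management Plan, and ties nothing to that band.
- That total exposure is understated by a known percentage. This needs withdrawal times, which the documents do not give.
- That a subject who stops on Day 10 but attends Visit 4 goes unnoticed. With full use until then, compliance is 20/168 = 12%, which shows the non-use even though exposure reads 84 days.

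**Conclusion.** The point holds for subjects who withdraw before Visit 4 and attend no later visit. The stated rule gives a wrong result for them: 0 days and no compliance value if they leave after Visit 2 without another visit, and only the days to Visit 3 (39 to 45) if they leave after it. A programmer might set the first case to missing instead of 0; compliance has no value either way.

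The consequence is limited to description: the Safety exposure and compliance tables (14.2.1.2.1 and 14.2.1.1.1), the mITT compliance table (14.2.1.1.2) for those who leave after Visit 3, and the listings. Withdrawers with no post-baseline efficacy measurement are outside mITT. The primary BI analysis is unchanged, and so are the adverse event tables, which use counts and percentages without person-time.

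The 22 to 47 is an allowance for reaching about 128 evaluable completers, not a forecast of withdrawals. The examples assume two uses a day where full use is stated, and Visit 3 on Day 42 unless another day is shown.

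**What to change.** In SAP 4.3.1, for subjects who discontinue before Visit 4:

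1. End the last interval at the CRF withdrawal date, as SAP 4.1.1 already does.
2. For exposure, use the date of last recorded product use where the diary shows an earlier one. Protocol 7.1 secures the withdrawal date but not the last-use date, so for subjects lost to follow-up with no diary, flag that the end date is the administrative withdrawal date and may overstate use.
3. For compliance, run the denominator to the withdrawal date, not to last use, and count occasions over that same interval. Closing it at last use would hide non-use: full use to Day 10 and withdrawal on Day 40 would score 20/(10 × 2) = 100%, whereas the withdrawal date gives 20/(40 × 2) = 25%.
4. If the diary is not returned, show compliance for that interval as missing and report the number of such subjects.
5. State whether an optional final visit or an unplanned visit counts as the last available visit, and how a Day 0 withdrawal is handled; end date minus start date still gives 0 there.

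The Day 30 withdrawer with use to that day then has 30 days of exposure. For the Day 75 withdrawer, full use gives 75 days and 150/150 = 100%; no use after Visit 3 gives 84/150 = 56%.

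The cost is a few lines of SAP text and programming before database lock, and some approximate end dates for subjects lost to follow-up.

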#### **4.3.2 Prior and Concomitant Medication**

Prior or concomitant medication taken by or administered to a subject will be recorded in the case report form. The prior and concomitant medications will be coded using an internal validated medication dictionary, [CCI](#).

Prior medication and prior non-drug therapies will be listed by subject, with drug name, GSK drug synonym, reason for medication, dose, frequency, route, start date, study day relative to the study treatment start date (Visit 2) and end date ([Listing 16.2.4.4](#)). Prior medications are defined as those which stopped before the study treatment start date (Visit 2). If the stop date is unknown or incomplete and the medication cannot be considered as stopped prior to study treatment start date (Visit 2) then the medication will be considered as a concomitant medication.

Concomitant medications and concomitant non-drug therapies will be listed similarly ([Listing 16.2.4.5](#)) with either ongoing or end date displayed. Concomitant medications are defined as medications that started or stopped on or after the study treatment start date (Visit 2), or are ongoing.

For the assignment of prior and concomitant medications, the randomization date will be used as the study treatment start date for subjects randomized to the No Intervention Group.

Unknown dates will not be imputed, however if the start or stop date is unknown, then it will be assumed to be concomitant medication unless the partial start date or stop date indicates differently.

## 4.4 Analysis of Efficacy

### 4.4.1 Primary Efficacy Endpoint

#### 4.4.1.1 Primary Efficacy Endpoint Definition

The primary efficacy endpoint is the BI score at Week 12. The BI score for each subject will be calculated as the average index value over all tooth sites scored as follows:

- BI Score = Sum of index values over all evaluable tooth sites/Number of evaluable tooth sites.

The BI score has a range of 0 to 2.

The BI will be assessed on the facial and lingual gingival surfaces of each scorable tooth. Three scores should be recorded buccally/labially (distal, body, mesial sites) and three scores lingually/palatally (distal, body, mesial sites). The BI will be assessed by the same examiner on all evaluable teeth at Baseline (Visit 2), Week 6 (Visit 3) and Week 12 (Visit 4).

The BI scoring system is described in [Table 4-2](#).

**Table 4-2 The Bleeding Index**

Score	Description
0	Absence of bleeding on probing
1	Bleeding observed within 30 seconds of probing
2	Bleeding observed immediately on probing

#### 4.4.1.2 Statistical Hypothesis, Model, and Method of Analysis

The primary analysis is a comparison of the BI score between the Intervention Group and No Intervention Group at Week 12 for subjects eligible for the mITT population.

The null and alternative hypotheses to be tested in the primary analyses are:

$H_0$ : There is no treatment difference in mean BI score after 12 weeks

$H_1$ : There is a treatment difference in mean BI score after 12 weeks

An Analysis of Covariance (ANCOVA) model will be used for the primary analysis with treatment group, gender, denture material type (acrylic or cobalt chrome), and baseline mean overall MGI score (low, high) as factors and the baseline BI score as a covariate. The adjusted means and standard errors (SEs) of the two treatment groups together with the treatment difference, SE, 95% confidence interval of the difference, between-group p-value and the proportionate reduction will be provided in [Table 14.2.2.1.2](#) for the mITT population.

The proportionate reduction will be calculated as:

- Proportionate reduction =  $[(\text{Adjusted Mean of No Intervention Group} - \text{Adjusted Mean of Intervention Group}) / \text{Adjusted Mean of No Intervention Group}] * 100$ .

The assumption of normality and homogeneity of variance in the ANCOVA model will be investigated and if violated, data transformations will be investigated. If suitable transformations cannot be found, non-parametric tests will be performed, and results will be compared with the ANCOVA results. If the inferences from the two analyses are similar, then both sets of results will be reported and emphasis will be made on the ANCOVA results. In case of discrepancies between inferences of the ANCOVA and non-parametric analysis, results will be drawn from the non-parametric analysis.

Descriptive statistics (n, mean, SD, SE, median, minimum, maximum) of the primary variable will be provided at Baseline, Week 6 and Week 12 visits by treatment group (and overall for Baseline only) for the mITT population ([Table 14.2.2.1.1](#)).

The raw mean and SE of the BI score (whole mouth and associated with abutment teeth) will be presented graphically over time for each treatment group in [Figure 14.2.1.1](#) (mITT population).

The BI value obtained for each tooth, surface and site will be listed by subject and visit in [Listing 16.2.6.1](#) for all randomized subjects. The BI score will also be listed by subject and visit in [Listing 16.2.6.6.1](#) for all randomized subjects.

